10.3.12. Visual Function Questionnaire (VFQ-25)

Participant-reported visual function will be assessed with the National Eye Institute (NEI) Visual Functioning Questionnaire 25 (VFQ-25, see Appendix 2) at Screening/Baseline, Year 1, Year 3, and Year 5 visits. The VFQ-25 will be administered by site study personnel.

11. PROTOCOL DEVIATIONS

Protocol deviations must be reported by the Study Site to the DCC within five business days.

Sites will be notified of protocol deviations discovered during data monitoring and source

document verification. Study Sites must also submit protocol deviations to their IRB pursuant to their IRB policy.

12. ADVERSE EVENTS

An adverse event (AE) is any untoward medical occurrence in a participant who is administered a test article. The AE does not necessarily have a causal relationship with the treatment. An AE can therefore be any unfavorable and unintended sign (including an abnormal laboratory finding), symptom, or disease temporally associated with study treatments.

A nonserious AE is defined as a change in a participant's ophthalmic and/or medical health that is not life-threatening, does not require hospitalization, does not prolong a current hospitalization and is not disabling. All AEs must be reported to the DCC using REDCap. All AEs must be reported whether they are considered study-related or not.

12.1. Serious Adverse Events

A serious adverse event is defined as any adverse experience occurring at any time during the study that results in:

- Death
- Life-threatening
- Inpatient hospitalization
- Prolongation of existing hospitalization
- Disability or permanent damage (including vision threatening complications)
- A congenital anomaly/birth defect
- Required intervention to prevent permanent impairment or damage and/or other serious important medical events

SAEs will be documented the same as adverse events, but flagged as a SAE. All SAEs should be submitted in REDCap within five business days of the Investigator's knowledge of the event. When new significant information is obtained as well as when the outcome of an event is known, the Investigator must provide updates in REDCap. If the participant is hospitalized, a deidentified copy of the discharge summary must be uploaded into the REDCap system as soon as it becomes available. All SAEs must be submitted to the sites IRB pursuant to their IRB policy.

12.2. Recording Instructions

Mild, moderate, or severe should be used to describe the maximum intensity of the event.

- Mild – Does not interfere with the participant's usual functions
- Moderate – Interferes to some extent with the participant's usual functions
- Severe – Interferes significantly with the participant's usual functions

It should be noted that a severe intensity does not necessarily mean it is an SAE.

The investigator will also be asked to determine the likelihood of the relationship between the study intervention and the AE.

12.3. Follow-up of Adverse Events

For participants who have ongoing ocular adverse events at the time of their exit visit, it is recommended that the Investigator schedule a follow-up visit to determine the outcome of the event.

13. MONITORING

Complete source documents will be monitored for the first participant enrolled in the study at each site and randomly thereafter. A deidentified copy of the source document will be submitted to DCC for source verification. Random monitoring of 10% of study visits will be performed; monitoring of additional study visits will be undertaken based on performance and queries. Deidentified source documents must be provided upon DCC request. Onsite monitoring visits may be required if Study Sites are unresponsive to DCC requests or excessive discrepancies are found.

14. DATA AND SAFETY MONITORING BOARD

Throughout the course of the study, all adverse events will be monitored and reported on an adverse event case report form, including seriousness, action taken and relationship to study treatment. A Data and Safety Monitoring Board (DSMB), independent from the study, will review all serious adverse events (SAE). The committee members will be selected for this study by the Chair, [name], based on their experience and qualifications. If adverse events occur, the first concern will be the safety of the study participant. For additional details of the conduct and procedures for the DSMB please see the DSMB charter.

15. WITHDRAWAL OF STUDY PARTICIPANT

If a participant wishes to withdraw from the study, the reason for withdrawal should be documented in the source document and REDCap. An exit visit should be performed if possible. If a participant does not return for a scheduled visit, every effort should be made to contact the participant and document the participant's outcome.

Relevant tests and assessments should be performed according to the schedule for Year 5/Exit visit if withdrawal occurs between surgery and Year 5 visits.

16. DATA ANALYSIS

16.1. *Interim Analysis/Safety Monitoring*

A number of interim analyses will be performed. The purpose of these analyses will be:

- a. To monitor recruitment targets in subgroups of interest (NVG vs non-NVG) and to monitor balance between treatment groups with regard to prognostic factors.
- b. To provide a regular mechanism for evaluating data quality, protocol adherence, and side-effect patterns including adverse reactions.
- c. To determine whether the study should be terminated early. Negative results could suggest that there is no possibility of ever establishing significance between-group differences.
- d. To assess the possibility that a positive but nonsignificant trend might require an increase in the originally projected sample size or an increase in the study duration.

Interim analyses will be performed every 3 months for the first year of enrollment and every 6 months thereafter. Interim analyses may also be performed at any time upon the request of the DSMB. The DCC will provide the results to the DSMB for making all decisions regarding the future conduct of the study. All investigators will be masked as to the results of interim analyses.

16.2. *Primary Analysis*

In the primary analysis, the null hypothesis is that there is no difference in one-year cumulative failure rates between the SAS group and the TLC group. The cumulative failure rates will be compared with Fisher exact test with one degree of freedom. The survival time from the treatment to failure will be estimated by Kaplan-Meier survival curve for each group and compared between the two treatment groups with the log-rank test. The potential effect of covariates will be assessed with the Cox proportional hazards models.

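### Section 16.1(d) lets a between-group trend enlarge or extend the trial and 16.2 then tests without adjustment, so the protocol/SAP does not assure the 5% type I error

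*Combined protocol and SAP*

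**What the plan says.** Section 16.1 gives four purposes for the interim analyses. Item (d) is worded as judging whether "a positive but nonsignificant trend might require an increase in the originally projected sample size or an increase in the study duration". Item (c) concerns early termination and gives only a futility reason: "Negative results could suggest that there is no possibility of ever establishing significance between-group differences".

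The looks are frequent: "Interim analyses will be performed every 3 months for the first year of enrollment and every 6 months thereafter". In addition, "Interim analyses may also be performed at any time upon the request of the DSMB". On authority: "The DCC will provide the results to the DSMB for making all decisions regarding the future conduct of the study". On masking: "All investigators will be masked as to the results of interim analyses".

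In section 16.2, "the null hypothesis is that there is no difference in one-year cumulative failure rates between the SAS group and the TLC group". The test is stated without qualification: "The cumulative failure rates will be compared with Fisher exact test with one degree of freedom". A log-rank comparison of time to failure follows, also with no adjustment.

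The only stated alpha is the 5% in section 7.4, within a fixed-sample calculation. The multiplicity paragraph at the end of section 16.3.5 is framed around safety measures and safety looks, names no method, and sends its results to the monitoring committee. Section 14 leaves DSMB procedures to a charter that was not supplied.

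**The concern.** If the final sample size or follow-up depends on the observed treatment difference, the usual test statistic no longer has its fixed-design null distribution. A trial that just misses can be enlarged and tested again at the same level. Item (d) names that situation, gives the DSMB the results, and sets no trigger, maximum, timing or number of increases. Section 16.2 does not say how the final test would account for it.

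At stake is whether a positive result obtained after such a change could be defended. Masking the investigators protects trial conduct; it does not correct a test whose sample size was chosen from the comparative result. A rule written after the change could not fully answer the challenge.

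**Working it through.** **1. The plan's own figure.** Inputs from section 7.4: 50% v 30% failure at five years, 80% power, alpha 5%. With a two-sided test and unpooled variance, n per arm = (1.960 + 0.842)² × (0.5×0.5 + 0.3×0.7) / 0.20² = 7.85 × 0.46 / 0.04 = 90.3, so 91. Then 182 / 0.65 = 280. The plan's figures reproduce. The 5% behaves as a two-sided, fixed-sample level.

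**2. When the looks carry information.** Assume uniform accrual over the planned year (section 7.5) and on-time visits. The share of participants past day 365 is 0 at month 12, 0.50 at month 18 and 1.0 at month 24. If Month 12 visits fall at the late window edge (day 547, Table 1), it is 0.50 at month 24 and 1.0 at month 30. Treatment may follow baseline by up to 45 days (section 8.1), so these times are approximate. Both informative looks at the one-year outcome come after planned recruitment closes. Longer follow-up adds nothing to a one-year outcome; it adds events only to the log-rank test.

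For the log-rank test, fit a piecewise exponential through 21% at one year and 50% at five years (section 7.4), with no dropout. The share of final events is 0.51 at month 24, 0.74 at month 42, 0.88 at month 54, 0.94 at month 60 and 1.0 at month 72.

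**3. Assumptions the plan does not supply.** One increase, by a factor k = 1.25, 1.5 or 2. The trigger is either an interim p between 0.05 and 0.20, 0.30 or 0.50, or any nonsignificant trend. It acts in either direction or in one direction only. The final test is at unadjusted two-sided 5%.

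**4. Formulas.** Let t be the information fraction at the decision, A the set of interim results that trigger the increase, and c = 1.960. For a nominal-level test, the null error is

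∫ over z not in A of φ(z)R₁(z)dz + ∫ over z in A of φ(z)Rₖ(z)dz,

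where R_T(z) = 1 − Φ[(c√T − z√t)/√(T−t)] + Φ[(−c√T − z√t)/√(T−t)].

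At t = 1 the first part is 5.0%. For k = 2 and any nonsignificant trend the second part is 3.3%, total 8.3%. If only one direction triggers, half of that is added: 5.0 + 3.3/2 = 6.7%.

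For Fisher, the same sum is taken exactly over the binomial outcomes at 21% failure in both arms, with 91 and 140 per arm. Without any increase the size is 3.3% (91) and 3.6% (140).

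**5. Results (% type I error, one increase)**

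| Trigger | Fisher, half information | Fisher, full information | Nominal, half information | Nominal, final analysis |
|---|---|---|---|---|
| p from 0.05 to 0.20/0.30/0.50, either direction | 3.0–3.6 | 4.6–5.9 | 4.6–5.0 | 6.8–7.9 |
| Any nonsignificant trend, either direction | 3.6–4.5 | 4.9–6.3 | 5.3–5.8 | 7.1–8.3 |
| p from 0.05 to 0.20/0.30/0.50, one direction | 3.1–3.6 | 3.9–4.7 | 4.8–5.0 | 5.9–6.4 |
| Any nonsignificant trend, one direction | 3.5–3.9 | 4.1–4.9 | 5.2–5.4 | 6.0–6.7 |

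**6. Repeated increases.** Section 16.1 sets no cap. With two to four steps after the planned end, to 1.5–2 times the planned size and either direction, simulation gives 5.8–8.7% for Fisher and 8.3–11.2% for a nominal test.

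**7. Can extra log-rank events be had by waiting?** After year 1 the fitted hazard is ln(0.79/0.50)/4 = 0.114 per year. Raising events by 25% means going from 50% to 62.5% failed: ln(0.50/0.375)/0.114 = 2.5 more years. Raising them by 50% means 75% failed: ln(0.50/0.25)/0.114 = 6.1 more years. Doubling them would need every eye to fail.

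**The case against.** Item (d) is worded as a purpose, not a decision rule, and the charter may contain one. Both points are fair. The claim is therefore limited to what the protocol/SAP assures. But 16.1 also gives the DSMB all decisions on conduct, and a charter rule would still need a matching final test in 16.2.

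For the hypothesis that 16.2 states, the effect is close to nil. Fisher starts at 3.3–3.6% and exceeds 5% only if recruitment reopens once the one-year data are essentially complete, and only if a trend in either direction counts. The word positive in (d), with sizing on lower failure under TLC, could mean one direction, which keeps Fisher below 5%. This stands.

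The upper log-rank figures need 25–100% more events, which in practice means new recruitment or a very long extension. This also stands.

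Two broader readings are tempting:

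- A reader might infer that the many looks are repeated efficacy tests and that the error is badly inflated. The documents do not support this. Item (c) describes only futility stopping, which does not inflate the error; efficacy stopping is neither described nor excluded. Even if looks could declare efficacy at a nominal 5%, the one-year test has about two informative looks, giving 5.1–5.7% with Fisher and 8.3% by normal theory.
- A reader might also infer that inflation can arise only from late decisions. That depends on the trigger. With any nonsignificant trend, a nominal test reaches 5.2–5.8% at half information. If recruitment ran past one year, such looks would fall during enrolment.

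**Conclusion.** The gap is real. As written, the protocol/SAP allows a comparative trend to change the size or duration of the trial and specifies no final test that holds 5% under such a change. The documents do not show that the error will exceed 5%; they show that it is not controlled.

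For a single increase the excess is at most about 1.3 percentage points with Fisher (6.3% against 5%) and 3.3 points for a log-rank-type test at the final analysis (8.3% against 5%). Several plausible settings give no excess. These sizes rest on the assumed trigger, direction, factor of increase, accrual pattern and single increase, none of which 16.1 settles. More than one increase would make them larger. The normal-theory figures stand in for the log-rank test. This is a cheap improvement, not a flaw that undermines the design.

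**What to change.** In section 16.1 replace item (d) with: *Sample size or study duration may be changed only on the basis of the masked pooled failure rate and retention.* Add: *Interim looks serve safety, conduct and non-binding futility; there is no stopping for efficacy.* Align the DSMB charter with both sentences. This needs no extra participants. The cost is that the trial gives up reacting to a between-group trend.

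If the sponsor wants to keep that option, prespecify a single increase, its timing and its cap, and state which test is protected, the one-year Fisher test or the log-rank test. Then choose one of two routes:

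- A fixed-weight (inverse-normal) combination test, Z = √w·Z₁ + √(1−w)·Z₂, with w set in advance and Z₁, Z₂ from the data before and after the decision. This returned 5.0% at information fractions 0.25, 0.5, 0.75 and 0.9, whatever the second-stage size.
- An increase only within a prespecified conditional-power zone. With 50–80% under the current trend, the unadjusted nominal test stayed at 4.2–5.1%, above 5.0% only at information fraction 0.1.

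Either route adds some analysis work, and any increase adds participants or follow-up.

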3. BACKGROUND INFORMATION

Aqueous shunts (AS) are commonly used to treat eyes with glaucoma refractory to medical therapy or eyes that have failed or are at high risk of failing a filtering procedure. The Tube Versus Trabeculectomy (TVT) Study demonstrated that AS were more effective in the long term (5 years) than trabeculectomy in eyes with prior incisional surgery and uncontrolled glaucoma.² Largely due to the results of TVT, the frequency of AS implantation has increased 410% between 1994 and 2012.¹ Additionally, it led to the question being evaluated in the Primary Tube Versus Trabeculectomy (PTVT) Study whether primary AS surgery may be appropriate in treating uncontrolled primary open-angle glaucoma, which may further increase the rates of implantation. Despite the favorable results compared to trabeculectomy, approximately 30-50% of AS fail within the first 5 years of implantation.^{2, 3}

For eyes where an initial AS fails to control IOP and medical therapy is ineffective, two surgical techniques are often used -- implantation of a second AS or cyclodestruction. Regrettably, there is very little clinical evidence to direct care in cases of initial AS failure. Published studies investigating these two approaches separately conclude that both of these procedures are valid options for eyes with failed initial AS,⁴⁻¹¹ in that they are successful in lowering IOP. However, these studies are small and retrospective, with the exception of one small, non-comparative, prospective case series.¹²

Two retrospective studies published compared second AS with cyclodestruction after a failed initial AS: one with 17 eyes (8 AS, 9 cyclodestruction) in pediatric patients,¹³ and the other with 47 eyes (15 AS, 32 cyclodestruction) predominantly in adults.¹⁴ Both studies reported reduction of IOP and number of IOP-lowering medications in both treatment groups. The latter study showed that eyes treated with cyclodestruction had a higher early failure rate (mean 13.5 months), while the second AS group had few early failures, but a higher rate of long-term failures and complications (mean = 6.1 years).¹⁴ While these studies provide the best current clinical guidance for eyes that have failed an initial AS, there is no prospective, randomized, controlled clinical trial evaluating the efficacy or safety of these two treatment options, nor are there any data on the effects of these interventions in this setting on quality of life.

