7.4. Sample Size Calculations

The definition of success/failure in this study is similar to the Ahmed versus Baerveldt Comparison (ABC) study.³ In the ABC study, the 1- and 5-year failure rate for the primary Baerveldt tube shunt group was 14% and 34%, respectively. Anticipated failure rate for the SAS group is 50% more than the primary tube shunt (~21%=14% x1.5 for 1 year, and 50% = 34%x1.5 for 5 years). Setting the power at 80% and alpha at 5%, a sample size of **91** participants in each group (182 total) would allow us to detect a difference of 20% or more reduction in cumulative incidence of failures in the TLC group from an anticipated 50% failure at 5 years in the SAS group (i.e. <30% in TLC vs 50% in SAS).

The retention rate in the ABC study was 65% at the 5-year visit. A total of **280** participants would allow for a 35% dropout rate (or deaths) during the 5-year study period.

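### The primary null hypothesis is set at one year, but the sample size and its 80% power are derived only for the 5-year comparison, so the stated power does not apply to the stated null

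*Combined protocol and SAP*

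**What the plan says.** - **Section 16.2 (Primary Analysis)** states one null hypothesis: "the null hypothesis is that there is no difference in one-year cumulative failure rates between the SAS group and the TLC group". The next sentence is "The cumulative failure rates will be compared with Fisher exact test with one degree of freedom". Time to failure is then to be "estimated by Kaplan-Meier survival curve for each group and compared between the two treatment groups with the log-rank test". Nothing says which of the two tests decides.
- **Section 7.4 (Sample Size Calculations)** anticipates SAS failure of "21%=14% x1.5 for 1 year, and 50% = 34%x1.5 for 5 years". The 80% power and 91 per group are for a reduction of 20 points "in the TLC group from an anticipated 50% failure at 5 years in the SAS group", that is, 50% against 30%. The one-year figure of 21% is not used again. Enrolling 280 "would allow for a 35% dropout rate (or deaths) during the 5-year study period".
- **Sections 4.1 and 5** name failure at 1, 3 and 5 years together, with no order among them.
- **Section 16.1(d)** lets an interim look assess whether "a positive but nonsignificant trend might require an increase in the originally projected sample size or an increase in the study duration", without naming a time point or a test for that trend.
- **The multiplicity paragraph at the end of 16.3.5** concerns safety measures and interim safety looks, not the three primary time points.

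**The concern.** A power statement is useful only for the comparison it was computed for. Here it belongs to the 5-year contrast, while the only primary null in the plan is at one year. The reader is told neither what difference the one-year test can detect nor which comparison is the trial's answer.

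The choice could change the conclusion. Section 3 reports, from one retrospective study of 47 eyes, that "eyes treated with cyclodestruction had a higher early failure rate (mean 13.5 months), while the second AS group had few early failures", with more long-term failures in the second-shunt group. If that pattern held, the one-year and 5-year differences could differ in size or even in direction. A one-year Fisher test, a log-rank test and a 5-year comparison could then disagree. Without a rule set in advance, the deciding comparison could be picked after the results are known.

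**Working it through.** **1. Reproduce the plan's figure.** Inputs from 7.4: 50% against 30% at 5 years, power 80%, alpha 5%. Sidedness is not stated; two-sided is assumed. Normal approximation with unpooled variance:

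n = (1.960 + 0.842)² × (0.5×0.5 + 0.3×0.7) / 0.2² = 90.26, rounded up to 91 per group.

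A one-sided calculation (pooled variance) would give 74, so two-sided fits. Allowing for loss, 182 / 0.65 = 280. Both figures in 7.4 reproduce, and both rest on the 5-year contrast alone.

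**2. What the one-year test could detect.** The only one-year input in the documents is SAS at 21%. Power of Fisher's exact test is the sum, over all tables with two-sided p ≤ 0.05, of the product of the two binomial probabilities. The TLC rates that give about 80% power are:

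| Evaluable per arm | TLC at or below | TLC at or above |
|---|---|---|
| 91 | about 6.2% | about 41% |
| 140 (all 280, no loss by year 1) | 8.6% | 36.8% |

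**3. Illustrations at one year.** The documents give no one-year TLC rate, so each rate below is an assumption.

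- Same relative reduction as at 5 years: 0.21 × 30/50 = 12.6%.
- Same hazard ratio as at 5 years: ln 0.7 / ln 0.5 = 0.515, giving 1 − 0.79^0.515 = 11.4%.
- A 20-point difference against TLC: 21% + 20 = 41%.

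| One-year TLC rate | Fisher power, 91 per arm | Fisher power, 140 per arm |
|---|---|---|
| 12.6% | 26% | 41% |
| 11.4% | 35% | 53% |
| 41% | 80% | 94% |

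Modestly higher TLC failure of 25% or 30% gives 10% or 36% power with 140 per arm. One-year power therefore runs from very low to ample, depending on a rate that the plan does not state.

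**4. The 5-year comparison depends on the test.** Fisher's exact test on 91 per arm at 50% against 30% has 75.0% power, not 80%, because 91 comes from the normal approximation.

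For time-to-event methods, trials were simulated under these assumptions: 140 per arm; SAS failure 21% at 1 year and 50% at 5 years; TLC 30% at 5 years; hazards constant within each period and changing at 1 year; loss at a constant rate reaching 35% at 5 years.

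- Kaplan-Meier difference at 5 years, failures detected as they occur: about 87–90% power.
- The same comparison, with failures found only at scheduled visits spread over the Table 1 windows in section 10.1.2: about 70–77%.
- Log-rank test, failures detected as they occur: about 90% under proportional hazards (one-year TLC 11.4%), falling to about 62–64% if one-year TLC failure is 25%.

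The scheduled-visit case is pessimistic. Section 10.1.4 also lets IOP failure be picked up at non-study visits, and a reoperation can occur at any time.

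**The case against.** The strongest defence has four parts.

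- **Five years is already in the primary aim.** Sections 4.1 and 5 include it, 7.4 powers it, and the log-rank test can use the full follow-up. So the 5-year comparison does have a place in the plan. What it lacks is a rank and a stated null, and this part of the defence supplies neither.
- **The Fisher test is not undated.** A reader might infer that no year is attached to it. The Fisher sentence directly follows the one-year null, so the natural reading is a one-year test. That stands, and it sharpens the mismatch with 7.4.
- **The one-year test may have enough power.** A reader might infer from the illustrations that it is underpowered. The documents do not support that. A 20-point difference against TLC (21% against 41%) would have 80% power with 91 per arm and 94% with 140. Section 3 gives no one-year rate for either procedure, its mean time to early failure of 13.5 months lies beyond one year, and the study compared only 15 with 32 eyes. It shows that the time point may matter, not what the one-year TLC rate will be.
- **Section 16.1(d) allows the trial to be enlarged or extended.** This helps only partly, since the trend it refers to has no time point or test.

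**Conclusion.** The point holds as a mismatch within the plan. The one stated primary null is at one year, the only power calculation is at 5 years, and no section reconciles them or says which comparison decides. This rests on the text alone and needs no assumption about failure rates.

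The size of the gap cannot be fixed from the documents. It can be bounded: with SAS at 21% and a two-sided Fisher test, about 80% power at one year requires TLC failure outside roughly 6.2% to 41% (91 per arm), or outside 8.6% to 36.8% (140 per arm, no loss).

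Two stronger readings should be avoided. First, the 91 and 280 are not miscalculated; they reproduce for the contrast they were built on. Second, the higher simulated 5-year power of 87–90% is not a figure the protocol can simply adopt. It depends on how failures are ascertained, and falls to about 70–77% if they are found only at scheduled visits.

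**What to change.** Make sections 4.1, 5, 7.4 and 16.2 name the same deciding time point and test, and state power for that comparison with its assumptions. Any one of these would do:

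- **(a) Make 5-year cumulative failure primary, matching 7.4.** Report 1- and 3-year estimates with 95% confidence intervals. If Fisher's test on 91 evaluable per arm is used, restate the power as 75%. If a Kaplan-Meier or log-rank comparison is used, compute its power under stated loss, visit-schedule and hazard assumptions before printing it.
- **(b) Keep one year primary.** Replace the 80% claim with the one-year detectable difference for a stated number evaluable, using the limits in step 2 of the working or their equivalent for another number. Label the 5-year power as that of a secondary comparison.
- **(c) Keep all three time points.** State a testing order or multiplicity rule, and say which comparison the power statement covers.

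Whichever is chosen, 16.1(d) should say that its trend refers to the same comparison.

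The cost is wording and restated figures, with no added patients or visits. Under (a) the confirmatory answer comes only at 5 years. Under (b), or with Fisher's test kept at 5 years, a stated power figure becomes less favourable. Under (c) a fixed order can block later comparisons, or a split alpha lowers power.

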6.2. Exclusion Criteria

Patients who meet the following exclusion criteria may NOT be enrolled:

1. Monocular
2. Presence of more than one AS *in the study eye*
3. Previous cyclodestruction *in the study eye*
4. Presence of active iris neovascularization *in the study eye*
5. Binocular diplopia
6. Presence of scleral buckle *in the study eye*
7. History of scleritis in either eye
8. History of scleromalacia *in the study eye*
9. Insufficient conjunctiva to cover AS in the *study eye*
10. IOP cannot be accurately measured with Goldmann applanation, Pneumotonometer, or Tono-Pen *in the study eye* (e.g. keratoprosthesis)

11. Presence of silicone oil *in the study eye*
12. Presence of retinal detachment *in the study eye*
13. Presence of intraocular or orbital tumor affecting *the study eye*
14. Need for cataract extraction or concurrent procedure at the time of study treatment, except tectonic aqueous shunt revisions for both groups is allowed
15. In the opinion of the investigator, should not be enrolled in this study (e.g. uncontrolled systemic diseases, altered mental status, etc.)
16. Unwilling or unable to give consent and satisfy requirements of the study (e.g. accept randomization, follow-up for 5 years, etc.)

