7. STUDY DESIGN CONSIDERATIONS

7.1. Stratification

Eyes will be classified into neovascular glaucoma (NVG) or non-NVG group based on glaucoma diagnosis for the purposes of generalizability.

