7.2. Randomization Scheme

An adaptive block randomization scheme will be implemented with a block size of 4 and balancing between NVG and non-NVG strata within each site.

Upon completion of the Screening/Baseline visit, the study eye will be randomly assigned to one of the 2 treatment groups: SAS or TLC within each stratum (NVG vs non-NVG) and each site based on the computer generated assignment.

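### The named tests use neither the NVG randomisation stratum nor the collected baseline values: a cheap gain in precision, not an error

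*Combined protocol and SAP*

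**What the plan says.** All references are to the combined protocol and SAP.

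- **Randomisation (7.1, 7.2).** Assignment is made "within each stratum (NVG vs non-NVG) and each site based on the computer generated assignment", in blocks of 4. The reason given for the strata is breadth of population: "Eyes will be classified into neovascular glaucoma (NVG) or non-NVG group based on glaucoma diagnosis for the purposes of generalizability".
- **Primary analysis (16.2).** "The cumulative failure rates will be compared with Fisher exact test with one degree of freedom". Time to failure is "estimated by Kaplan-Meier survival curve for each group and compared between the two treatment groups with the log-rank test". The only mention of covariates is "The potential effect of covariates will be assessed with the Cox proportional hazards models", with no covariate listed.
- **VFQ-25 and BCVA (16.3.1, 16.3.3).** Each has a t-test or Wilcoxon test at single visits and a repeated-measures mixed model. Neither section names a baseline term. Section 4.2 states both aims as changes from baseline.
- **Sample size (7.4).** 91 per group, at 80% power and 5% alpha, from "an anticipated 50% failure at 5 years in the SAS group (i.e. <30% in TLC vs 50% in SAS").
- **Data (7.2, Table 2).** NVG status is needed to randomise. VFQ-25 and visual acuity are measured at Screening/Baseline.

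**The concern.** A factor that is balanced by design but left out of the analysis usually gives away a little power: the balance reduces chance variation, and the unstratified test does not credit it. The loss grows with how strongly NVG predicts failure. The same logic applies to a continuous outcome with a measured baseline, where an adjusted comparison is generally at least as precise as a raw change score.

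At stake is precision in a trial planned at 80% power with 35% expected loss, where no new data would be needed to recover it. Naming the terms in advance also removes analyst choice, since the Cox covariates are open and so is the choice between t-test and Wilcoxon.

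**Working it through.** **1. The plan's sample size.** Two-sided 5% is assumed, because sidedness is not stated. With unpooled variances, n = (1.960 + 0.842)² × (0.50×0.50 + 0.30×0.70) / 0.20² = 7.849 × 0.46 / 0.04 = 90.3, so 91 per group. Then 182 / 0.65 = 280. Both figures reproduce. The formula is a normal approximation, not Fisher's test.

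**2. Fisher against the uncorrected chi-square, with no stratum involved.** Exact enumeration at 50% vs 30%, two-sided 5%:

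| Evaluable per arm | Fisher | Chi-square | Difference (points) |
|---|---|---|---|
| 91 : 91 | 75.0% | 79.4% | 4.4 |
| 91 : 92 | 77.3% | 79.8% | 2.5 |
| 90 : 92 | 76.3% | 78.6% | 2.3 |
| 88 : 94 | 77.6% | 79.5% | 1.9 |

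The 4.4-point gap belongs to exactly equal arms. Evaluable numbers after 35% loss will rarely be exactly equal, so about 2 to 2.5 points is realistic. At 91 : 91 with a common rate of 50%, the actual level is 3.15% for Fisher and 4.53% for chi-square.

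**3. What the NVG stratum adds.** The documents give neither the NVG share nor its effect on failure, so both are assumed. Simulation: 280 eyes, 70 sites, blocks of 4 within site and NVG, 35% lost at random, overall failure 50% vs 30%, 6,000 replicates.

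| NVG share, hazard ratio (HR) | Fisher | Chi-square | CMH by NVG | CMH minus chi-square (points) |
|---|---|---|---|---|
| 10%, HR 2 | 77.3% | 79.7% | 80.2% | 0.5 |
| 20%, HR 2 | 76.2% | 78.5% | 79.3% | 0.8 |
| 30%, HR 2 | 77.3% | 80.1% | 81.1% | 1.0 |
| 20%, HR 3 | 76.2% | 78.4% | 81.0% | 2.6 |

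At HR 1 the difference is -0.1 to -0.3 point. Across shares of 10-30%, HR 3 gives 1 to 3 points. A separate calculation using odds ratios of 1 to 5, with arms fixed at 91, gave about 0 to 3 points.

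For the log-rank test (8,000 replicates, 35% exponential loss by 5 years), unstratified against stratified power is 90.2 vs 90.7%, 90.4 vs 91.5% and 89.7 vs 91.2% at HR 2 with 10, 20 and 30% NVG. It is 90.6 vs 93.1% at HR 3 with 20% NVG.

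**4. Baseline adjustment.** Let r be the baseline to follow-up correlation and k the ratio of follow-up SD to baseline SD. With a slope fitted separately at each visit, the variance cut against a change score is 1 - k²(1 - r²) / (k² + 1 - 2rk).

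| r (assumed) | 0.5 | 0.6 | 0.7 | 0.8 |
|---|---|---|---|---|
| k = 1 | 25.0% | 20.0% | 15.0% | 10.0% |
| k = 1.25 | 10.7% | 5.9% | 1.9% | 0.0% |

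Example, k = 1 and r = 0.5: 1 - 0.75 / 1 = 25%. The cut is zero where k = 1/r. A wider follow-up spread is plausible for BCVA: entry requires hand motion or better (6.1), and eyes can later fall to light perception or none.

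These cuts need a baseline-by-visit term. Take k = 1.25, baseline correlations of 0.8, 0.7 and 0.5 at three successive visits, and between-visit correlations of 0.6 to 0.7, all assumed. With one common slope, the last-visit cut falls from 10.7% to 0.7-3.0%. At a between-visit correlation of 0.6, the first-visit variance is 0.6% larger than for a change score.

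**The case against.** The strongest reply is that the stratum is worth almost nothing. At HR 2 or below it moves CMH power by -0.3 to +1.0 point, and NVG may be a weak predictor here, because "Presence of active iris neovascularization" in the study eye is an exclusion (6.2). Section 16.2 also already plans a Cox model that could carry NVG, and an unstratified log-rank test with about 90% power in the simulations above. The mixed models may include baseline; the text does not say. All of this stands. It limits the point to a small improvement and, for the mixed models, to under-specification rather than a shown loss.

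Three stronger readings are tempting, and the documents do not support them.

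- **The tests are invalid because they ignore the stratum.** They are not. Leaving out a balanced stratum makes them, if anything, conservative.
- **Ignoring NVG reduces power to 75%.** That figure comes from Fisher's conservatism at exactly 91 : 91 and has nothing to do with stratification.
- **The primary one-year comparison is short of power by a known amount.** Section 16.2 sets its null hypothesis at one year, but 7.4 gives no one-year TLC rate and section 3 cites more early failures after cyclodestruction. No one-year power follows, so every power figure here is for the 5-year design point.

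Site is also a randomisation factor. With up to 70 sites and two strata, 280 / 140 = 2 eyes per cell if all sites enrol, so stratifying a test on every site is not workable. NVG alone is.

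**Conclusion.** The point holds as a low-cost improvement that should be made; it is not an error in the plan. The textual facts are clear: NVG is a randomisation stratum that the Fisher and log-rank tests do not use, and no baseline covariate is named for two outcomes whose aims are changes from baseline.

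The gains are modest and should be kept apart. NVG itself gives about 0 to 1 point of power at HR 2 or below and 1 to 3 points at HR 3. Leaving Fisher's test gives about 2 to 2.5 points. Baseline adjustment ranges from nothing to a 25% variance cut. NVG share, NVG effect, correlations and SD ratios are all assumptions. They decide how large the gain is; if NVG is not prognostic, the stratum gives no gain and a trivial loss.

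**What to change.** **Section 16.2.** Compare failure proportions with a CMH test stratified by NVG, and report a stratum-weighted risk difference with a 95% CI. Keep Fisher's test, and an analysis adjusted for site, as sensitivity analyses. Stratify the log-rank test by NVG. Stratify the Cox model by NVG for the treatment effect; where the NVG effect itself is wanted, fit a second model with NVG as a covariate.

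**Sections 16.3.1 and 16.3.3.** Take the visit-wise contrasts from the planned repeated-measures model with baseline value, visit, baseline-by-visit, arm, arm-by-visit and NVG, and an unstructured covariance. Keep the Wilcoxon test on change from baseline as a sensitivity analysis, because VFQ-25 subscales are bounded and BCVA includes eyes below chart level.

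**Cost.** Wording only, with no new data. CMH is asymptotic and gives up Fisher's guaranteed level: simulated type I error was 4.6-5.6% (Monte Carlo SE 0.3), against 3.7-4.7% for Fisher. The plan already accepts an asymptotic chi-square test for complications (16.3.2). Stratified log-rank and Cox analyses address a within-stratum effect. If NVG is not prognostic, stratifying costs about 0 to 0.3 point of power.
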